9.4.10 Restricted Medications

Subjects will be directed to discontinue current urate-lowering therapy at least 7 days prior to Day 1.

Subjects should not receive the following medications from Screening through the end of pegloticase and MTX during the trial:

- Concomitant therapy with allopurinol, febuxostat, probenecid or other urate-lowering medications or a PEG-conjugated drug (see [Appendix 17.10](#));
- Other investigational agents;

- Any MTX other than the trial approved investigational product, azathioprine, mycophenolate mofetil or other systemic immunosuppressants aside from glucocorticoids for gout flare or IR prophylaxis or intermittent gout flare treatment;
- Systemic or radiologic treatment for ongoing cancer, excluding non-melanoma skin cancer; and
- Current or chronic treatment with systemic immunosuppressive agents.

9.4.11 Treatment Compliance

A dosing calendar will be provided to subjects at the Week -6 Visit for recording the MTX dose and the date, time and mg dose of each dose. The dosing calendar and MTX auto-injector should be brought to each trial visit for assessment of compliance. At the end of the trial or if the subject prematurely discontinues the trial, the subjects will return any unused or partially used trial drugs to the site. Adherence to the MTX regimen will also be recorded by the trial coordinator at trial visits in the eCRF by recording the date of each MTX dose (mg), frequency and time of each dose per calendar day. Subjects who have injected at least 80% of the protocol-specified amount of MTX will be considered compliant. Noncompliant subjects will be re-educated on compliance.

At trial visits, the subject will be asked whether folic acid, gout flare and IR prophylaxis were administered.

Pegloticase will be administered at the trial site by trained personnel. The date and time of infusion start and stop and the stop and start time of the flush will be recorded.

9.4.12 Contraception Requirements

Women of childbearing potential (including those with an onset of menopause <2 years prior to Screening, non-therapy-induced amenorrhea for <12 months prior to Screening or not surgically sterile [absence of ovaries and/or uterus]) must agree to use 2 reliable forms of contraception during the trial, 1 of which is recommended to be hormonal, such as an oral contraceptive.

Hormonal contraception must be started ≥ 1 full cycle prior to Week -6 (start of MTX) and continue for 30 days after the last dose of pegloticase, or at least 1 ovulatory cycle after the last dose of MTX (whichever is the longer duration after the last dose of pegloticase). Highly effective contraceptive methods (with a failure rate <1% per year), when used consistently and correctly, include implants, injectables, combined oral contraceptives, some intrauterine devices, sexual abstinence or vasectomized partner.

Men who are not vasectomized must agree to use appropriate contraception so as to not impregnate a female partner of reproductive potential during the trial, beginning with the initiation of MTX at Week -6 and continuing for at least 3 months after the last dose of MTX. Appropriate contraception methods include condom use and abstinence.

9.5 Efficacy, Quality-of-Life, Pharmacokinetic and Safety Variables

The Schedule of Assessments is provided in [Section 2.1](#).

9.5.1 Efficacy Variables

Efficacy will be assessed based on measurement of sUA levels, urate deposition and **CCI**

and the HAQ-DI, HAQ pain scale and HAQ health scale.

9.5.1.1 Serum Uric Acid

Serum samples for measurement of sUA levels will be collected at the Screening Visit, the Week -6 Visit (prior to the first dose of MTX) and the Week -2 Visit. On Day 1, a pre- and post-infusion sUA will be collected to be shipped to the central laboratory. For the remainder of trial visits beginning at Week 2 during the Pegloticase + MTX Treatment Period; 2 sUA samples will be collected within 48 hours PRIOR to each pegloticase infusion. One sample will be for testing at the site's local laboratory and the second sample will be sent to the central laboratory (the central laboratory sample may be drawn separately from the local collection). The local laboratory or central laboratory pre-infusion sUA results should be reported prior to pegloticase infusion. Note: It is allowable for the local and central laboratory sUA samples to be drawn on different days or times so long as both samples are drawn within 48 hours PRIOR to the infusion and the results of at least 1 sample are available prior to the infusion. Additional serum samples for sUA levels will be collected after the end of each pegloticase infusion prior to discharge at Weeks 10, 12, 14, 20, 22, 32, 34, 44 and 46; at Weeks 21 and 23; and at the End of Pegloticase (if applicable) or the Week 24 or 48/End of Trial/Early Termination Visit.

Serum for sUA analysis will also be collected following the first 7 pegloticase infusions at Day 1, Week 2, Week 4, Week 6, Week 8, Week 10 and Week 12, respectively. The sUA will be collected at the following non-infusion days: 1st (~24 hours), 4th (~96 hours), 7th (~168 hours) and 10th (~240 hours) day after each of the first 4 infusions, Day 1 to Week 6. Following Week 8, Week 10, Week 12, sUA will be collected at the following non-infusion days: 1st (~24 hours) and 7th (~168 hours). If infusion intervals of less than 2 weeks should occur due to scheduling issues, less than 4 sUA measurements between infusions are acceptable. The 1st day (~24 hours) samples must be obtained at a minimum. If there are restrictions in relation to obtaining the interim samples also obtain 7th day (~168 hours) if feasible.

To ease the on-site visit burden for subjects, for non infusion visit sUA collection, a Home Health Care nurse may collect sUA samples, AE data and concomitant medication information if the subject consents

Prior to Week 22, subjects whose lowest available interim sUA value (typically the 1st day [~24 hours] after infusion) after the pegloticase infusion at Week 2, 4, 6, 8, 10 or 12 is less than a 50% reduction from the highest sUA value measured between Screening and pre-infusion on Day 1 will discontinue treatment and complete the End of Pegloticase Visit within 2 weeks of the last infusion, but remain in the trial for biweekly visits, including the Week 24/End of Trial/Early Termination and 30-Day Post-Treatment Follow-up Visits.

Samples that result in discordant results between local and central laboratories will be evaluated and discussed with the Investigator and the Sponsor's Medical Monitor on a case-by-case basis to determine whether the subject should continue on trial or proceed to the End of Pegloticase Visit.

9.5.1.2 Dual-energy Computed Tomography

A DECT (at a minimum, hands, feet and knees; other anatomical areas, as clinically indicated) will be obtained during the MTX Run-in Period and prior to the Day 1 Visit; prior to pegloticase infusion at the Week 14 and Week 24 Visits; and at the End of Pegloticase (if applicable) and Week 24 or 48/End of Trial/Early Termination Visits. After the initial DECT scan, the DECT at all other scheduled time points may be completed within ± 10 days of the scheduled time point.

Subjects who end pegloticase infusions prior to Week 24 should follow the scheduled time points and have a DECT scan at the End of Pegloticase (if applicable) and Week 24/End of Trial/Early Termination Visits (detailed guidance is provided within the Imaging Manual).

The imaging will be performed by a trial-specific, qualified radiologist.

9.5.1.3 CCI

[REDACTED]

9.5.1.4 CCI

[REDACTED]

CCI

[REDACTED]

CCI [REDACTED]

CCI
CCI

9.5.1.6 Health Assessment Questionnaire

The HAQ ([Appendix 17.2](#)) including the HAQ-DI, pain and health scales, will be administered at the Week -6 Visit (prior to the first dose of MTX); prior to pegloticase infusion at the Day 1, Weeks 6, 14 and 20 Visits (Pegloticase + MTX Treatment Period); prior to pegloticase infusion at the Weeks 24 and 36 Visits (subjects who may gain further benefit beyond 12 infusions and elect to receive pegloticase + MTX during the Optional Pegloticase + MTX Extension Period); and at the End of Pegloticase (if applicable) and Week 24 or 48/End of Trial/Early Termination Visits ([Section 2.1](#)).

The HAQ-DI is a self-report functional status instrument that can be filled out by a subject in less than 5 minutes and requires 1 minute to score. The index measures disability over the past week by asking a total of 20 questions covering 8 domains of function: dressing and grooming, arising, eating, walking, hygiene, reach, grip, and usual activities. There are at least 2 questions in each domain and the 8 domains represent a comprehensive set of functional activities. The HAQ-DI is calculated by scoring the answer to each question in the HAQ from 0 to 3, with 0 representing the ability to do without any difficulty, and 3 representing inability to do. Any activity that requires assistance from another individual or requires the use of an assistive device raises a 0 or 1 score to a 2. The highest score for each of the 8 domains is summed (range from 0 to 24) and divided by 8 to yield, on a scale with 25 possible values, a Functional Disability Index with a range from 0 to 3. The disability index is based on the number of domains answered and is computed only if the subject completes answers to at least 6 domains ([Bruce](#) and Fries, 2003).

The HAQ pain scale asks subjects to record how much pain they have had in the past week on a scale of 0 to 100, where zero represents “no pain” and 100 represents “severe pain.”

The HAQ health scale is a measure of overall health. Subjects are asked to rate how well they are doing on a score of 0 to 100, where zero represents “very well” and 100 represents “very poor” health.

9.5.1.7 CCI [REDACTED]

CCI [REDACTED]

CCI

9.5.2 CCI

CCI

9.5.2.1 CCI

CCI

9.5.2.2 CCI

CCI

CCI

9.5.2.3 CCI

CCI

9.5.3 CCI

Serum samples for CCI will be collected after the end of infusion on Day 1 (prior to discharge); prior to the pegloticase infusion and after the end of infusion (prior to discharge) at the Weeks 2, 6, 14 and 22 Visits (Pegloticase + MTX Treatment Period); prior to the pegloticase infusion and after the end of infusion at the Week 36 Visit (subjects who may gain further benefit beyond 12 infusions and elect to receive pegloticase + MTX during the Optional Pegloticase + MTX Extension Period); and at the End of Pegloticase (if applicable) or Week 24 or 48/End of Trial/Early Termination Visit.

Serum samples for evaluation of CCI will be collected at the Week -6 Visit (prior to the first dose of MTX); prior to the pegloticase infusion on Day 1 and at the Weeks 2, 6, 14 and 22 Visits (Pegloticase + MTX Treatment Period); prior to the pegloticase infusion and after the end of infusion at the Week 36 Visit (subjects who may gain further benefit beyond 12 infusions and elect to receive pegloticase + MTX during the Optional Pegloticase + MTX Extension Period); and at the End of Pegloticase (if applicable) or Week 24 or 48/End of Trial/Early Termination Visit.

Blood samples for CCI analysis will be collected prior to the pegloticase infusion on Day 1 and at the Weeks 14 and 22 Visits (Pegloticase + MTX Treatment Period) and prior to the pegloticase infusion at the Weeks 24, 36 and 46 Visits (subjects who may gain further benefit beyond 12 infusions and elect to receive pegloticase + MTX during the Optional Pegloticase + MTX Extension Period).

Each sample collection date and time will be recorded in source documents and the eCRF.

Detailed instructions regarding blood sample timing and handling are provided in the Laboratory Manual.

9.5.3.1 Additional Sample Collection for Future Use

Optional serum and urine samples will be collected from each consenting subject at the Week -6 Visit (prior to the first dose of MTX); prior to pegloticase infusion at the Day 1 and Week 14

Visits (Pegloticase + MTX Treatment Period); prior to pegloticase infusion at the Week 24 and Week 36 Visits (subjects who may gain further benefit beyond 12 infusions and elect to receive pegloticase + MTX during the Optional Pegloticase + MTX Extension Period); and at the End of Pegloticase (if applicable) and Week 24 or 48/End of Trial/Early Termination Visits.

Subjects may still participate in the trial even if they decline to provide consent for the optional future use of serum and urine samples.

Samples will be retained for potential future analyses, which may include biomarkers relevant to gout (e.g., inflammatory markers), gout co-morbidities in response to pegloticase or other potential treatments for gout.

The samples will be retained no longer than 15 years after trial completion or as required by applicable law. The samples will be stored in a secured storage space with adequate measures to protect confidentiality.

Detailed instructions regarding blood sample timing and handling are provided in the Laboratory Manual.

9.5.4 Safety Variables

Safety assessments will include monitoring and recording of all AEs, whether or not drug related, measurement of vital signs, physical examinations and monitoring of hematology and blood chemistry and urine test.

9.5.4.1 Adverse Events

9.5.4.1.1 Definitions

9.5.4.1.1.1 Adverse Event Definition

As defined by the ICH, an AE is any untoward medical occurrence in a clinical trial subject administered a medicinal (investigational or non-investigational) product, whether or not the event is considered related to the trial drug. An AE is therefore any unfavorable and unintended sign (including an abnormal laboratory finding, except for an abnormal sUA result), symptom, or disease (new or exacerbated) temporally associated with the use of the trial drug. This includes any occurrence that is new in onset or aggravated in severity or frequency from the Baseline condition, or abnormal results of diagnostic procedures, including laboratory test abnormalities.

Examples of an AE include:

- Conditions newly detected or diagnosed after the signing of the ICF, including conditions that may have been present but undetected prior to the start of the trial;
- Conditions known to have been present prior to the start of the trial that worsen after the signing of the ICF;
- Signs, symptoms or the clinical sequelae of a suspected drug interaction; and

- Signs, symptoms or the clinical sequelae of a suspected overdose of either investigational product or a concomitant medication (overdose per se should not be reported as an AE).

Issues that will not be considered an AE include:

- Conditions present at the start of the trial should be recorded as medical history;
- Medical or surgical procedures (e.g., endoscopy, appendectomy; however, a condition that leads to a procedure is an AE if it qualifies according to the definitions above);
- Situations where an untoward medical occurrence did not occur (e.g., social, diagnostic, elective or convenience admission to a hospital);
- Fluctuations of pre-existing disease(s) or condition(s) present or detected at the start of the trial that do not represent a clinically significant change from Baseline; and
- Abnormal laboratory or test findings that are not assessed by the Investigator as a clinically significant change from Baseline.

AEs are divided into the categories “serious” and “non-serious.” This determines the procedures that must be used to report/document the AE.

9.5.4.1.1.2 Serious Adverse Event Definition

Based on ICH guidelines, an SAE is any untoward medical occurrence that at any dose:

- a. Results in death.
- b. Is life threatening.

NOTE: The term ‘life threatening’ in the definition of ‘serious’ refers to an event in which the subject was at risk of death at the time of the event. It does not refer to an event that hypothetically might have caused death if it were more severe, prolonged, or untreated.

- c. Requires hospitalization or prolongation of existing hospitalization.

NOTE: Hospitalization signifies that the subject has been admitted to the hospital as an inpatient for any length of time. Treatment on an emergency, outpatient basis for an event not fulfilling any of the definitions of SAEs and not resulting in hospital admission does not qualify for this category but may be appropriately included in category g (see below). Complications that occur during hospitalization are usually AEs. If a complication prolongs hospitalization or fulfills any other serious criterion, the event will be considered as serious. When in doubt as to whether ‘hospitalization’ occurred, consult the Sponsor’s Medical Monitor.

Hospitalization will not be considered an AE in and of itself. It will be considered an outcome of an AE. Therefore, if there is no associated AE, there is no SAE. For example, hospitalization for elective or pre-planned treatment of a pre-existing condition that did not worsen from Baseline will not be considered an AE.

d. Results in persistent or significant disability/incapacity.

NOTE: The term disability means a substantial disruption of a person's ability to conduct normal life functions. This definition is not intended to include experiences of relatively minor medical significance, such as uncomplicated headache, nausea, vomiting, diarrhea, influenza and accidental trauma (e.g., sprained ankle) that may temporarily interfere with or prevent everyday life functions but do not constitute a substantial disruption.

e. Is a congenital anomaly/birth defect.

f. Is a suspected transmission of any infectious agent via a medicinal product.

g. Is an important medical event.

NOTE: Medical and scientific judgment should be exercised in deciding whether expedited reporting as serious is appropriate in other situations; specifically, important medical events that may not be immediately life threatening or result in death or hospitalization but may jeopardize the subject or may require medical or surgical intervention to prevent 1 of the other outcomes listed in the above definition should usually be considered serious. Examples of such events are invasive cancers, intensive treatment in an emergency room or at home for allergic bronchospasm, blood dyscrasias, or convulsions that do not result in hospitalization or development of drug dependency or drug abuse. If in doubt as to whether or not an event qualifies as an 'important medical event,' consult the Sponsor's Medical Monitor.

9.5.4.1.1.3 Non-Serious Adverse Event Definition

AEs that do not result in any of the outcomes listed in [Section 9.5.4.1.1.2](#) are considered non-serious.

9.5.4.1.1.4 Unexpected Adverse Event Definition

An AE or suspected adverse reaction is considered unexpected if it is not listed in the Reference Safety Information section of the Investigator's Brochure (for pegloticase) or United States Prescribing Information (for MTX) or is not listed with the specificity or severity that has been observed. Unexpected, as used in this definition, also refers to AEs or suspected adverse reactions that are mentioned in the Reference Safety Information as occurring with a class of drugs or as anticipated from the pharmacological properties of the drug, but are not specifically mentioned as occurring with the particular drug under investigation.

9.5.4.1.1.5 Adverse Events of Special Interest

AESIs include IRs, anaphylaxis, gout flares and MACE. If 3 events of Anaphylaxis (as assessed by PI) occur an Adjudication Committee (composed of independent experts external to Horizon) will be established for this trial to adjudicate AESI's of Anaphylaxis. The AESI of IR, MACE and gout flare will not be adjudicated.

Tolerability Criteria

Safety assessments of IR and anaphylaxis will be conducted after 7 and 10 subjects in Cohort 1 complete 6 infusions and after 3, 6, 10, 15 and 20 subjects in Cohort 2 complete 6 infusions. If more than one-third of subjects experience a severe IR and/or anaphylaxis related to pegloticase infusion, the pegloticase infusions will be considered not tolerated.

The signs and symptoms of severe IRs are usually prolonged (e.g., not rapidly responsive to symptomatic medication and/or brief interruption of infusion) or recurrent following initial improvement. Possible associated signs and symptoms of IRs may include, but not be limited to:

- Respiratory: difficulty breathing with wheezing or stridor; respiratory distress manifested as at least 2 or more of the following: tachypnoea, increased use of accessory respiratory muscles, cyanosis, recession or grunting;
- Upper airway swelling (lip, tongue, throat, uvula or larynx);
- Cardiovascular: hypertension, tachycardia, measured hypotension, a decreased level of consciousness or loss of consciousness;
- Dermatological or mucosal: generalized urticaria (hives), generalized erythema, angioedema or generalized pruritus with skin rash

The Safety Review Team must confirm that the tolerability criteria are not met in Cohort 1, prior to Screening subjects with history of pegloticase-related mild IR for Cohort 2. The Safety Review Team could stop the trial for other significant safety concerns.

If an anaphylaxis event occurs in any subject, further dosing with pegloticase for that subject will be discontinued. Anaphylaxis events will be adjudicated using the Sampson criteria (see [Appendix Error! Reference source not found.](#) for guidance on anaphylaxis and IR symptoms and assessment).

Infusion Reaction

An IR will be defined as any infusion-related AE or cluster of temporally-related AEs, not attributable to another cause, which occur during the pegloticase infusion and for up to 2 hours post infusion. Other AEs that occur outside of the 2-hour window following the infusion may also be categorized as an IR at the Principal Investigator's discretion. Signs and symptoms of the IR and treatments administered will be documented in the medical record and in the eCRF and will be adjudicated.

Examples of AEs not considered possible IRs include, but are not limited to: laboratory abnormalities that are unlikely to have occurred during or within 1 hour following the infusion (e.g., anemia), gout flares, most infectious diseases or the recurrence or worsening of a known chronic medical problem identified in the subject's medical history.

In the event of any potential or suspected IR, the procedures in [Section 9.4.9.2](#) will be performed.

Anaphylaxis

Any incidence of anaphylaxis should be reported as an SAE. Anaphylaxis will be defined using the National Institute of Allergy and Infectious Diseases/Food Allergy and Anaphylaxis Network criteria ([Sampson et al, 2006](#)), and will be adjudicated:

1. Acute onset of an illness (minutes to several hours) with involvement of the skin, mucosal tissue, or both (e.g., generalized hives; pruritus or flushing; urticaria, and angioedema (of lips, tongue or uvula) and ≥ 1 of the following:
 - a. Respiratory compromise (e.g., dyspnea, wheeze-bronchospasm, stridor, reduced peak expiratory flow, hypoxemia) or
 - b. Reduced blood pressure or associated symptoms of end-organ dysfunction (e.g., hypotonia [collapse], syncope, incontinence)
2. Two or more of the following that occur rapidly after exposure to a likely allergen for that subject (minutes to several hours):
 - a. Involvement of the skin-mucosal tissue (e.g., generalized hives, itch-flush, swollen lips-tongue or uvula);
 - b. Respiratory compromise (e.g., dyspnea, wheeze-bronchospasm, stridor, reduced peak expiratory flow, hypoxemia);
 - c. Reduced blood pressure or associated symptoms (e.g., hypotonia [collapse], syncope, incontinence); or
 - d. Persistent gastrointestinal symptoms (e.g., crampy, abdominal pain, vomiting).
3. Reduced blood pressure after exposure to known allergen for that subject (minutes to several hours): systolic blood pressure <90 mmHg or $>30\%$ decrease from that subject's Baseline.

Gout Flares

It is common for potent urate-lowering therapies to lead to acute attacks of gout. Gout flares will be confirmed through questioning or direct observation detailed in [Section 9.5.4.8](#).

Cardiovascular Events

Cardiovascular AEs will be collected as part of the AE collection. External adjudication will be conducted for MACE (defined as non-fatal stroke, non-fatal myocardial infarction, cardiovascular death and congestive heart failure). Refer to the Adjudication Committee Charter for the detailed definition.

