9.5.6 Adjudication Committee

An Adjudication Committee (composed of independent experts external to Horizon) will be established for this trial to adjudicate the AESIs of anaphylaxis, if 3 events of Anaphylaxis (as assessed by PI) occur (see [Section 9.5.4.1.1.5](#)). The AESI of IR, MACE and gout flare will not be adjudicated. The AESIs of anaphylaxis will be adjudicated at a frequency defined in the Adjudication Committee Charter. The committee will be comprised of physicians with experience in immunology, allergic reactions, rheumatology and cardiovascular diseases. Details outlining the responsibilities of the Adjudication Committee will be included in the Adjudication Committee Charter.

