9.6.1.5 Safety and Tolerability Endpoints

Safety and tolerability endpoints are:

- The incidence of IRs, anaphylaxis, gout flares, MACE and the AE/SAE profile overall and potentially attributed to the combination of pegloticase and MTX.
- The mean change from Baseline in laboratory test results, including hs-CRP.
- The mean change from Baseline in vital sign results.

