14.3 Adverse Events of Special Interest

Adverse events of special interest will include infusion reactions (IRs), anaphylaxis, gout flares, and MACE including non-fatal myocardial infarction, non-fatal stroke, cardiovascular death, and congestive heart failure.

IRs and Anaphylaxis

IRs and anaphylaxis reactions are identified by the investigator on the eCRF. The signs and symptoms associated with each event are entered on the eCRF and will be coded to the MedDRA dictionary. IRs and anaphylaxis events, and the associated signs and symptoms, will be summarized in the pegloticase + MTX period by SOC, PT, severity, and the time relative to the most recent pegloticase infusion. Time relative to the most recent pegloticase infusion will be categorized as: during infusion, \leq 2 hours after infusion, $>$ 2 hours to 24 hours after infusion, $>$ 24 hours after infusion, and missing (time of event is missing).

If 3 or more events of anaphylaxis occur, events will also be reviewed by an external adjudication committee. Events as reviewed by the external adjudication committee will be summarized separately.

The following search algorithm will be used to identify possible IR and anaphylaxis cases:

Infusion Reaction

- All IRs reported by investigators based on the protocol definition and reported on the eCRF.
- All other AEs that occur after start of infusion and up to 24 hours following the end of the infusion or on the same day of infusion if the start time is missing.

Anaphylaxis

- Any anaphylaxis reported by investigators based on the NIAID/FAAN criteria and reported on the eCRF.
- Any anaphylactic reactions identified by the algorithmic MedDRA SMQ Anaphylactic reactions.

The number and percentage of subjects with IRs including anaphylaxis (investigator reported) will be summarized overall and by severity of event by the following categories for both **CCI**

[REDACTED]:

- **CCI** [REDACTED]
- [REDACTED]
 - [REDACTED]
 - [REDACTED]
 - [REDACTED]
- [REDACTED]
 - [REDACTED]
 - [REDACTED]

Cardiovascular Events

Cardiovascular events will include Major Adverse Cardiovascular Events (MACE), including non-fatal myocardial infarction, non-fatal stroke, cardiovascular death, and congestive heart failure. The following search algorithm will be used to identify possible MACE:

- For cardiovascular death any fatal case plus:

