- Standardized MedDRA Queries (SMQ): Myocardial infarction (broad), Haemorrhagic central nervous system vascular conditions (narrow), Ischaemic Central Nervous System (CNS) Vascular conditions (narrow), Central nervous system vascular disorders, not specified as haemorrhagic or ischaemic (narrow), Embolic and thrombotic events (arterial, venous, vessel type unspecified and mixed arterial and venous) (narrow), Cardiac failure (broad), Shock-associated circulatory or cardiac conditions (excl torsades de pointes) (broad), Torsade de pointes/QT prolongation (broad), Arrhythmia related investigations, signs and symptoms (broad), Cardiomyopathy (broad), Supraventricular tachyarrhythmias (narrow), Ventricular tachyarrhythmias (narrow), Conduction defects (narrow)
- All PTs under SOC of Cardiac disorders
- HLGT Aneurysm
- For non-fatal myocardial infarction: SMQ Myocardial infarction (broad)
- For non-fatal stroke: SMQ: Ischaemic Central Nervous System (CNS) Vascular conditions (narrow), Haemorrhagic central nervous system vascular conditions (narrow), Central nervous system vascular disorders, not specified as haemorrhagic or ischaemic (narrow)
- Congestive heart failure: SMQ Cardiac failure (broad)

Cardiovascular events will be tabulated only if 5 or more subjects have experienced a cardiovascular event. Cardiovascular events will be summarized by MedDRA SOC and PT in the MTX Analysis Set for the MTX Run-in Period and in the Safety Analysis Set for the pegloticase + MTX period.

Gout Flares

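### The documents disagree on whether MACE is adjudicated, and the SAP neither confirms search hits nor tabulates them below 5 subjects, so the MACE incidence endpoint has two competing numerators and may get no table

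*Protocol*

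**What the plan says.** MACE is one of the adverse events of special interest (AESIs). It has four components: congestive heart failure, cardiovascular death, and non-fatal infarction or stroke. Protocol 9.6.1.5 makes its incidence a safety endpoint: "The incidence of IRs, anaphylaxis, gout flares, MACE and the AE/SAE profile overall". Protocol 9.6.7 plans to summarize the proportion of subjects with each AESI and sets no minimum count.

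On adjudication, the cardiovascular paragraph of Protocol 9.5.4.1.1.5 says "External adjudication will be conducted for MACE" and then "Refer to the Adjudication Committee Charter for the detailed definition". The opening paragraph of the same section says "The AESI of IR, MACE and gout flare will not be adjudicated". That sentence also appears in the synopsis, Protocol 9.1, Protocol 9.5.6 and SAP section 4.

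Under Protocol 9.5.6 the committee is set up to "adjudicate the AESIs of anaphylaxis, if 3 events of Anaphylaxis (as assessed by PI) occur". Its members are to be "physicians with experience in immunology, allergic reactions, rheumatology and cardiovascular diseases".

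SAP 14.3 introduces its cardiovascular search with "The following search algorithm will be used to identify possible MACE" and names MedDRA queries for each component. It then says "Cardiovascular events will be summarized by MedDRA SOC and PT", but only if at least 5 subjects have had such an event. All AESIs are also listed. SAP section 15 reports no change from the protocol's analyses.

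**The concern.** Two people working from these documents could produce different MACE counts, and each could cite current text. One would wait for adjudicated events; the other would run the search and count the hits. The SAP calls the hits possible MACE and does not say who decides whether a hit is MACE. For anaphylaxis, by contrast, SAP 14.3 plans a separate summary of adjudicated events if the committee is formed.

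The 5-subject condition adds a second problem. In a trial of 30, a moderate number of cardiovascular events would never reach a MACE table, although the protocol promises the proportion.

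This matters for interpretation. Protocol 7.1.2.6 lists exacerbation of congestive heart failure among the risks of pegloticase, and heart failure is a MACE component. In 30 subjects, classifying one subject differently moves the proportion by 1/30 = 3.3 percentage points.

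**Working it through.** **Step 1. Statements on adjudication of MACE, both documents.**

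| Place | MACE adjudicated? |
|---|---|
| Protocol 9.5.4.1.1.5, cardiovascular paragraph | Yes, externally |
| Protocol synopsis, trial design | No |
| Protocol 9.1 | No |
| Protocol 9.5.4.1.1.5, opening paragraph | No |
| Protocol 9.5.6 | No |
| SAP section 4 | No |

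The count is one against five. All six are current text, and two of them stand in the same section.

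**Step 2. Where the detailed definition sits.** The cardiovascular paragraph sends the reader to the Adjudication Committee Charter. The committee is formed only after 3 investigator-assessed anaphylaxis events, and then for anaphylaxis alone. To illustrate, take the 6.5% anaphylaxis rate in Protocol 7.1.2, n = 30 and at most one event per subject. Then P(3 or more) = 1 − Σ(k=0..2) C(30,k) × 0.065^k × 0.935^(30−k) = 30.9%. Over an assumed 1% to 10% it runs from 0.3% to 58.9%.

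**Step 3. From search to summary.** SAP 14.3 goes from possible MACE by named queries, to cardiovascular events, to a table by SOC and PT. No step between the first and the last compares a hit with the four components.

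**Step 4. The threshold against the protocol.** Protocol 9.6.7 gives the proportion for each AESI with no condition. SAP 14.3 gives a table only at 5 or more subjects, otherwise a listing. SAP section 15 declares no change.

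**Step 5. What the threshold does at n = 30.** The documents give no MACE rate or precision to reproduce. The exact (Clopper-Pearson) interval was checked on the plan's one comparable figure: 12/30 gives a lower bound of 22.7%, against the stated approximately 23% (Protocol 9.6.9).

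The lower bound is the 2.5% point of Beta(x, n−x+1), and the upper bound is the 97.5% point of Beta(x+1, n−x).

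- Largest count with no table: 4/30 = 13.3%, CI 3.8% to 30.7%.
- Smallest count with a table: 5/30 = 16.7%, CI 5.6% to 34.7%.

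For an assumed true proportion p of subjects with a cardiovascular event as the SAP counts it, P(table) = 1 − Σ(k=0..4) C(30,k) × p^k × (1−p)^(30−k). The chance of 1 to 4 affected subjects, so events but no table, is 1 − P(table) − (1−p)^30.

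| Assumed p | P(5 or more: table) | P(1 to 4: events, no table) |
|---|---|---|
| 2% | 0.03% | 45.4% |
| 5% | 1.6% | 77.0% |
| 10% | 17.5% | 78.2% |
| 15% | 47.6% | 51.7% |
| 20% | 74.5% | 25.4% |

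**The case against.** The strongest reply is that the intent is clear. Five statements agree, including the section devoted to the committee and the SAP. The single contrary sentence looks like a leftover, and a MedDRA search is a reasonable method for events that are not adjudicated. That is a fair account of the probable intent. It does not settle the matter, because the contrary sentence is current text, it carries the only pointer to a detailed definition, and the committee is still described with cardiovascular expertise.

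Several stronger readings are tempting, and the documents do not support them:

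- A reader might infer that MACE has no defined numerator at all. The SAP search is programmable, has queries for each component, and fits the five statements.
- A reader might infer that the protocol promises a rate for each component. It promises the incidence of MACE and the proportion with each AESI; the components are only the definition.
- A reader might expect one false hit to turn a reported 0/30 into 1/30. Below 5 subjects there is no table, and SAP 14.3 plans no confidence interval for cardiovascular events.
- The search limb that takes every cardiac-class term looks very broad, but it applies to fatal cases only.
- A reader might infer that events would be hidden. All AEs, SAEs and AESIs are listed, and treatment-emergent events are tabulated by SOC and PT.

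Two limits remain. The charter is not available here, and the SAP's table index is redacted, so neither can show whether a MACE table or definition exists elsewhere. Confirmation of hits by the Medical Monitor is a proposal; neither document requires it.

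**Conclusion.** The point holds as a contradiction with two consequences. First, the documents leave adjudicated MACE and unconfirmed search hits as competing numerators, with the detailed definition assigned to the charter of a committee that may never be formed. Second, the SAP's 5-subject condition conflicts with Protocol 9.6.7 and is not declared as a change.

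Up to 4 of 30 subjects (13.3%) could have an event with no cardiovascular table. At assumed true rates of 2% to 10%, such a table would be produced with probability 0.03% to 17.5%. These probabilities assume 30 treated subjects, independence between subjects and the threshold applied to those 30; the rates are assumptions, because the documents give none.

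The number of search hits that would not be MACE cannot be derived from the documents. The effect is confined to a descriptive safety endpoint. The primary analysis, the sample size and the tolerability rule, which uses only infusion reactions and anaphylaxis, are unaffected.

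**What to change.** 1. Reconcile the cardiovascular paragraph of Protocol 9.5.4.1.1.5 with the synopsis, 9.1, the opening of 9.5.4.1.1.5, 9.5.6 and SAP section 4.
2. Put the detailed MACE definition in the protocol or SAP, so that it does not depend on the committee being formed.
3. In SAP 14.3, have the sponsor's Medical Monitor classify each search hit against the four components before database lock. If adjudication is kept, use the adjudicated events instead. List the hits that are not confirmed.
4. Remove the 5-subject threshold for MACE. Report the number and percentage of subjects with confirmed MACE, overall and by component, whatever the count. The component breakdown goes beyond what the protocol promises but follows directly from the classification.

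The cost is a wording change in the protocol, a short addition to the SAP, medical review of what should be a few events by existing staff, and one extra table. No new data collection is needed.
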